Clinical status evaluation with 9-point ordinal scale ^j	Х	Х	Х	Х	Х	Х	
Drug dispensation and administration ^k		Х	Days 2 through14	Days 15 through 28 (if applicable)			
Hematology (local laboratory assessments) ¹	X	Х	Days 3, 5, 7, 9, 11, 13 (while in hospital)	Х	Days 17, 19, 21, 23, 25, 27 (while in hospital)	X	
Clinical chemistry (local laboratory assessments) ¹	X	Х	Days 3, 5, 7, 9, 11, 13 (while in hospital)	Х	Days 17, 19, 21, 23, 25, 27 (while in hospital)	Х	
Inflammatory markers (ferritin, CRP, D-dimer, procalcitonin, IL-6 [if feasible]; local laboratory assessments) ¹	Х	Х	Days 3, 5, 7, 9, 11, 13 (while in hospital)	Х	Days 17, 19, 21, 23, 25, 27 (while in hospital)	Х	
Correlative serum collection (optional) ^m		Х	Day 7 only	Х			
Pregnancy test (local laboratory assessments) ⁿ	Х					Х	
Lung imaging (chest x-ray or CT scan) ^o	Х						
Adverse events	Х	Х	Х	Х	X	Х	Х
Prior/concomitant medications ^p	Х	Х	Х	Х	X	Х	
Surgeries and procedures ^p	Х	Х	Х	Х	Х	Х	
SOFA score ^q	Х	Х	Х	Х	Х	Х	
In-hospital outcomes ^r	Х	Х	Х	Х	Х	Х	Х

^a The Day 1 visit may occur on the same day as the screening visit. If this occurs, non-laboratory assessments that occur at both visits do not have to be repeated.

^b If treatment is approved to continue beyond the initial 14-day period (ie, Day 15 through 28), if needed, contact IRT to dispense additional study drug.

^c If participant is discharged from the hospital, the scheduled assessments may be performed remotely, via telephone.

- ^d A follow-up assessment for patient-reported AEs and in-hospital outcomes (if applicable) will be conducted 28 ± 3 days after the last dose of study treatment. If participant has been discharged, the assessment may be performed remotely, via telephone.
- e Participant must provide informed consent (and assent, if applicable) before any study assessment is performed; informed consent may be obtained from a health care proxy where appropriate.
- ^f Confirmation of SARS-CoV-2 infection \leq 3 weeks prior to randomization by any test with local regulatory approval. Confirmation prior to informed consent (and assent, if applicable) is acceptable. Viral load and antibody testing may be performed by any approved method and is only required if local capabilities allow; a consistent method and specimen source should be used at all timepoints.

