- ^g Vital signs will be collected once daily while hospitalized between 7:00 AM and 12:00 PM local time and include heart rate, respiratory rate, systolic and diastolic blood pressure, and body temperature. Not required after discharge.
- ^h Arterial blood gases will be collected during screening, within 6 hours of planned randomization, to assess PaO₂/FiO₂. Thereafter, ABGs will be performed daily while 1) the participant is receiving mechanical ventilation, OR 2) the participant has an arterial line. Parameters including pH, PaO₂, PaCO₂, and SaO₂ will be collected for each ABG. SpO₂ (pulse oximetry) will be recorded in the eCRF once daily while hospitalized. ABGs and SpO₂ not required after discharge.
- ¹ Ventilator settings (as applicable) will be collected once daily between 7:00 AM and 12:00 PM local time. Settings to be collected include mode, FiO₂, PEEP, VT, and respiratory rate. Dates of intubation and extubation (if applicable) will be recorded. Supplemental oxygen support post-extubation will be collected daily through Day 29, until hospital discharge.
- ^j If participant is discharged, a telephone call may be used to perform assessment. See Appendix B for scale.
- ^k Beginning at Day 15, the participant may continue treatment up to Day 28 at the discretion of the investigator and after approval by the sponsor medical monitor.
- ¹ Hematology, clinical chemistry, and markers of inflammation should be measured by the local laboratory. See Section 9.4.3 for required analytes. If participant is discharged, local laboratory assessments may be performed on Day 15 and/or Day 29 if feasible.
- ^m An optional serum sample will be collected at Day 1 (predose) and Day 7 and 15 for cytokine analysis. See Section 9.5.1 for collection, processing, storage and shipment instructions.
- ⁿ Pregnancy test: only for females of childbearing potential, serum pregnancy test (serum hCG) will be performed at screening assessment. Serum or urine test is acceptable at subsequent assessment(s).
- ° Screening chest imaging may be ≤ 2 days prior to Day 1.

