- P All medications, procedures, and significant non-drug therapies administered from randomization through Day 29 must be recorded on the appropriate eCRF. Additionally, antivirals and therapeutic agents administered for SaRS-CoV-2 infection/COVID-19 infection and treatments for COVID-19 pneumonia/ARDS administered within 14 days of randomization must also be recorded. If participant is discharged from the hospital, the scheduled assessments may be performed via telephone.
- ^q The SOFA score is to be determined per Appendix C. Not required after discharge from the ICU. SpO₂ method for calculating respiratory score may be used if arterial blood gases were not performed on corresponding assessment day.
- ^r In-hospital outcomes will be collected on eCRFs as outlined in Section 9.3.5.

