9.3. Efficacy

9.3.1. Clinical Status (9-Point Scale)

Assessment of clinical status using a 9-point ordinal scale (WHO 2020b) will be recorded at baseline on Day 1 and then again once daily every morning (between 7:00 AM and 12:00 PM local time) through Day 29 of the study period. If a participant is discharged from the hospital, the assessment will be made by phone (between 7:00 AM and 12:00 PM local time). Each day, the worst score for the previous day will be recorded (ie, on Day 3, Day 2 score is obtained and recorded as Day 2). The scale is shown in Table 7.

Participant State	Descriptor	Score
Uninfected	No clinical or virological evidence of infection	0
Ambulatory ^a	No limitation of activities	1
	Limitation of activities	2
Hospitalized Mild Disease	Hospitalized, no oxygen therapy (defined as $\text{SpO}_2 \ge 94\%$ on room air)	3
	Oxygen by mask or nasal prongs	4
Hospitalized	Non-invasive ventilation or high-flow oxygen	5
Severe Disease	Intubation and mechanical ventilation	6
	Ventilation + additional organ support – vasopressors, RRT, ECMO	7
Dead	Death	8

 Table 7:
 COVID-19 9-Point Ordinal Clinical Status

^a Defined as not in hospital or in hospital and ready for discharge.

If the participant dies, the date of death will be collected in the eCRF.

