9.3.5. In-Hospital Outcomes

In addition to endpoints mentioned above, the following in-hospital outcomes will be captured on eCRFs:

- Ventilator-free days
- ICU-free days
- Vasopressor-free days
- Hospital-free days
- Oxygen-free days

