## 7.4. Analysis of the Secondary Efficacy Parameters

### 7.4.1. In-Hospital Outcomes

The number of ventilator-free, ICU-free, oxygen-free, vasopressor-free, and hospital-free calendar days between Study Days 2 and 29 (inclusive) will be derived using the rules as outlined in [Table 4](#). Note that qualifying vasopressor medications (ie, ATC Class C01CA - adrenergic and dopaminergic agents) will be determined through blinded review of concomitant medications, with the list of medications qualifying as vasopressors included as a note to file prior to final database lock.

Outcome-free days between Days 2 and 29 will be summarized descriptively (mean, mean, standard deviation) with treatment-group statistical comparisons performed using a Kruskal-Wallis test. Participants with missing data that do not permit evaluation for all 28 days, but are known to be alive at Day 29, will have each such day treated as not event-free. Participants who die prior to or on Day 29 will have 0 assigned days for each event-free endpoint. Participants for whom Day 29 survival status cannot be ascertained will be missing from the analysis.

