**Table 4: In-Hospital Outcome Event-Free Days Variable Definition**

Endpoint	The Number of Study Days That a Participant Was Alive and...
Ventilator-free days	did not require mechanical ventilation. a
ICU-free days	is out of the ICU. a
Vasopressor-free days	without use of vasopressor therapy. a
Hospital-free days	is out of the hospital. a
Oxygen-free days	did not receive supplemental oxygen. a

a Participants who do not survive through Day 29 will have 0 assigned days.

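### Oxygen-free days: neither document says how days after hospital discharge are derived, and if home oxygen is not captured the SAP's missing-day rule scores them as not oxygen-free

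*SAP*

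**What the plan says.** - **Endpoint.** SAP 7.4.1 counts free days over Study Days 2 to 29. SAP Table 4 (and Protocol Table 11) defines an oxygen-free day as one on which the participant was alive and "did not receive supplemental oxygen". Deaths by Day 29 score 0.
- **Missing days.** SAP 7.4.1: participants whose data do not allow all 28 days to be evaluated "but are known to be alive at Day 29, will have each such day treated as not event-free". Live discharge is not treated separately.
- **Daily oxygen record.** The ventilator/oxygen-support footnote to Protocol Table 3: "Supplemental oxygen support post-extubation will be collected daily through Day 29, until hospital discharge".
- **Other possible sources.** Protocol 9.3.5 says "the following in-hospital outcomes will be captured on eCRFs", and its list includes oxygen-free days. Table 3 schedules these outcomes through Day 29 and at follow-up, with the note "In-hospital outcomes will be collected on eCRFs as outlined in Section 9.3.5". The follow-up contact for "patient-reported AEs and in-hospital outcomes (if applicable) will be conducted" may be by telephone after discharge. The therapy footnote adds: "All medications, procedures, and significant non-drug therapies administered from randomization through Day 29 must be recorded on the appropriate eCRF".
- **Telephone ordinal score.** It continues daily after discharge (Protocol 9.3.1). The ambulatory state is "Defined as not in hospital or in hospital and ready for discharge", and its two levels differ only by limitation of activities.

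**The concern.** The daily oxygen record stops at discharge, while the endpoint runs to Day 29 and counts unevaluable days against survivors. No passage connects the two. If no form records home oxygen, every day at home becomes a day not free of oxygen. A survivor who goes home on room air then loses credit that a survivor kept in hospital on room air retains.

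This would lower the score of a fast recovery and could dilute a real benefit on this measure. Even if a form does capture home oxygen, two analysts could follow the present text and derive very different scores for the same person. At stake is one of five free-day secondary measures, tested without multiplicity adjustment (SAP 3.2).

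**Working it through.** **1. Window.** 29 − 2 + 1 = 28 days, matching the SAP.

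**2. Sources for a post-discharge day.** The daily oxygen record ends at discharge. The in-hospital outcomes form and the therapy log run on, but no oxygen question or derivation is stated for either. The ordinal score cannot identify home oxygen. By contrast, SAP 7.4.1 does name its source for vasopressors (blinded review of concomitant medications).

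**3. One participant.** Let *o* be the first oxygen-free day and *d* the discharge day, for a survivor who stays off oxygen.

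- True score = 29 − *o* + 1.
- Literal score = *d* − *o* + 1 if the discharge day counts, or (*d* − 1) − *o* + 1 if not.
- Off Day 8, discharged Day 10: 10 − 8 + 1 = 3, or 9 − 8 + 1 = 2.
- Off Day 8, in hospital on Day 29: 29 − 8 + 1 = 22.
- Opposite error: someone discharged on Day 15 who uses home oxygen through Day 29 has no oxygen-free days after discharge, but gains 29 − 15 = 14 if discharge is taken to mean oxygen-free.

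**4. Population effect (illustration).** The documents give no weaning or discharge timings, so all of these are assumed.

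- Mortality is 60% placebo vs 40% treated (the planning rates in SAP 3.3). Arm sizes are 84 vs 42, from a 2:2:1 split of 211 (211 × 2/5 = 84.4; 211/5 = 42.2); actual arm sizes are not given.
- Extubation day, then days to weaning, then days to discharge: early N(12,5), N(4,2), N(6,3); mid N(16,6), N(5,3), N(8,4); late N(18,6), N(5,3), N(10,4). Whole days; extubation and first oxygen-free day no earlier than Day 2; intervals no less than 0.
- Placebo survivors discharged before Day 29: 85%, 47%, 28%.
- Treated shifts: (a) none; (b) weaning 4 days earlier, later stay unchanged; (c) weaning 2 days earlier and later stay 2 days shorter, so discharge 4 days earlier; (d) later stay 4 days shorter.
- 400,000 draws per arm for P(treated > placebo), ties half; 2,000 trials per case for Kruskal-Wallis (2-sided 0.05, in favour of treatment), Monte Carlo standard error at most 1.1 points.

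Literal results are shown as discharge day counted / not counted.

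| Timing, shift | P true | P literal | KW true | KW literal |
|---|---|---|---|---|
| Early (a) | 0.600 | 0.600 / 0.596 | 49% | 50 / 48% |
| Early (b) | 0.648 | 0.607 / 0.602 | 83% | 52 / 49% |
| Early (c) | 0.625 | 0.563 / 0.542 | 69% | 24 / 13% |
| Early (d) | 0.599 | 0.526 / 0.472 | 47% | 9 / 0.5% |
| Mid (a) | 0.590 | 0.590 / 0.588 | 42% | 41 / 39% |
| Mid (b) | 0.641 | 0.625 / 0.620 | 82% | 71 / 68% |
| Mid (c) | 0.617 | 0.589 / 0.573 | 64% | 42 / 31% |
| Mid (d) | 0.589 | 0.552 / 0.518 | 43% | 19 / 7.5% |
| Late (a) | 0.584 | 0.584 / 0.583 | 38% | 39 / 38% |
| Late (b) | 0.642 | 0.635 / 0.632 | 82% | 78 / 75% |
| Late (c) | 0.615 | 0.599 / 0.591 | 64% | 51 / 46% |
| Late (d) | 0.583 | 0.560 / 0.544 | 41% | 24 / 15% |

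On the rank scale the direction reverses only in early (d) with the discharge day not counted. Mean literal scores, treated vs placebo, are lower on treatment in early (d) (2.02 vs 2.65 counted; 1.44 vs 2.30 not counted) and in mid (d) (2.44 vs 2.47; 2.01 vs 2.26).

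**The case against.** The strongest reply is that the harm depends on a form that is not public. The in-hospital outcomes row has no discharge cut-off, whereas vital signs and blood gases are expressly not required after discharge. Oxygen-free days is itself listed as an eCRF item, and telephone contact is allowed for in-hospital outcomes and therapies. The protocol thus provides routes by which home oxygen could be recorded. This stands, and it makes the point conditional. It does not close the gap, because nothing says what is asked about oxygen or which record feeds the derivation.

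Second, the SAP rule concerns missing data, and it does not say that planned non-collection after discharge is missing. Nothing is said about collecting ventilator settings after discharge either, yet few would score home days as not ventilator-free. This also stands: the text has two materially different readings, so a reader who infers that the plan is shown to miscount home days goes further than the documents allow.

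Third, scoring unknown days against participants is a defensible prespecified choice, and every timing above is assumed. Both are fair. But a rule that lowers the score for earlier discharge on room air works against what the measure is meant to show, and the one-participant arithmetic needs no assumed distribution.

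**Conclusion.** The point holds as a minor, conditional one. The derivation of post-discharge oxygen days is unspecified. If home oxygen is not captured, the literal rule makes earlier discharge score lower among survivors weaned on the same day.

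The population size rests wholly on assumed timings. A mortality effect alone changes the chance of a favourable test by 2 to 3 points at most. Otherwise the loss grows with the share of survivors discharged before Day 29, and it arises when treatment speeds weaning, shortens the later stay, or both. A reader might infer that it matters only if most survivors leave early and the post-weaning stay is shortened. The table does not support that: early (b), with the later stay unchanged, falls from 83% to 52/49%, and mid (c), with 47% discharged, falls from 64% to 42/31%.

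Nor should this be extended to all five free-day measures. It is shown only for oxygen-free days; for hospital-free days, discharge itself settles the status, barring unrecorded readmission. Primary mortality is unaffected.

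**What to change.** Amend SAP 7.4.1 before unblinding, for oxygen-free days only:

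1. Name the eCRF that supplies oxygen use after discharge, if one does, and use it.
2. Where it gives no answer:
   - apply the missing-day rule only to in-hospital days;
   - count days after live discharge home off oxygen as oxygen-free, unless home oxygen or readmission is recorded;
   - count days after discharge on oxygen, or to another care facility with unknown oxygen status, as not oxygen-free unless a stop date is recorded.
3. State whether the discharge day counts.
4. Report the current rule as a sensitivity analysis.

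The cost is a few SAP sentences and one derivation change, with no new data collection. The downside is that unrecorded home oxygen would be credited as oxygen-free. The sensitivity analysis shows how far the result depends on the rule, but it does not bound a between-arm difference in unrecorded home oxygen.

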**Table 4: In-Hospital Outcome Event-Free Days Variable Definition**

Endpoint	The Number of Study Days That a Participant Was Alive and...
Ventilator-free days	did not require mechanical ventilation. a
ICU-free days	is out of the ICU. a
Vasopressor-free days	without use of vasopressor therapy. a
Hospital-free days	is out of the hospital. a
Oxygen-free days	did not receive supplemental oxygen. a

a Participants who do not survive through Day 29 will have 0 assigned days.

### 7.4.2. COVID-19 9-Point Ordinal Scale

The COVID-19 9-Point Ordinal Scale (see [Appendix B](#)) will be tabulated by study day, ordinal category, and treatment group. Participants with missing values due to death will be imputed to have Category 8 (death). Participants released from the hospital that are lost to follow-up will be considered missing with regards to this endpoint. Missing intermediate days between observations will be imputed to the worst (highest) category from the 2 nonmissing observations.

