9. VISIT SCHEDULE AND ASSESSMENTS

The SoA (see Table 3) lists all of the assessments and when they are performed. All data obtained from these assessments must be supported in the participant's source documentation. Any assessments outlined in Table 3 otherwise performed per standard of care may be used to satisfy study requirements.

Participants should be seen for all visits/assessments as outlined in the assessment schedule (see Table 3) or as close to the designated day/time as possible. Missed or omitted visits or assessments should not lead to automatic discontinuation. Participants who prematurely discontinue the study (see Section 10.1.1) for any reason should be scheduled for a visit (in person or remote) as soon as possible, at which time all of the assessments listed for the final visit will be performed. At this final visit, all dispensed investigational product should be reconciled, and the AE and concomitant medications should be recorded on the eCRF.

If a participant is discharged from the hospital during the study period, the clinical status evaluation with 9-point ordinal scale will be performed via telephone call (7:00 AM-12:00 PM local time) daily, except for Day 15 and Day 29 when it will be performed in clinic, when possible (telephone contact is an acceptable alternative for clinic visits). If the participant is unable to return to the clinic on Day 15 and Day 29, all scheduled assessments may be performed by telephone; local laboratory assessments may be performed on Day 15 and/or Day 29 if feasible.

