## APPENDIX B. COVID-19 9-POINT ORDINAL SCALE

Participant State	Descriptor	Score
Uninfected	No clinical or virological evidence of infection	0
Ambulatory a	No limitation of activities	1
	Limitation of activities	2
Hospitalized Mild Disease	Hospitalized, no oxygen therapy (defined as SpO 2 ≥ 94% on room air)	3
	Oxygen by mask or nasal prongs	4
Hospitalized Severe Disease	Noninvasive ventilation or high-flow oxygen	5
	Intubation and mechanical ventilation	6
	Ventilation + additional organ support – vasopressors, RRT, ECMO	7
Dead	Death	8

a Defined as not in hospital or in hospital and ready for discharge.

Source: [WHO 2020](#).

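### The SAP 7.4.2 gap rule lets a later death fill missing ordinal scores, so a participant alive on Day 15 can be scored Category 8 on Day 15

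*SAP*

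**What the plan says.** SAP 7.4.2 gives three rules for missing ordinal scores.

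- Death: "Participants with missing values due to death will be imputed to have Category 8 (death").
- Loss after discharge: "Participants released from the hospital that are lost to follow-up will be considered missing with regards to this endpoint".
- Gaps: "Missing intermediate days between observations will be imputed to the worst (highest) category from the 2 nonmissing observations".

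SAP Appendix B places death at 8. The worst category for a living participant is 7, described as "Ventilation + additional organ support – vasopressors, RRT, ECMO".

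Protocol 9.3.1 says the score "will be recorded at baseline on Day 1 and then again once daily every morning", through Day 29. It adds: "Each day, the worst score for the previous day will be recorded". It also says: "If the participant dies, the date of death will be collected in the eCRF". For participants who leave hospital during the study period, Protocol Section 9 says "the clinical status evaluation with 9-point ordinal scale will be performed via telephone call" each day, with Days 15 and 29 done in clinic where possible.

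SAP 7.4.2.1 and 7.4.2.2 use the Day 15 and Day 29 scores and add no further rule for missing values.

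**The concern.** A worst-neighbour rule is a reasonable conservative choice while both neighbours are living states. It behaves differently when the later neighbour is a death, because the value it carries back is a state the participant had not yet reached. Vital status before a death with a complete date is known, so the imputed value contradicts data the trial holds.

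Worst-case intent does not settle the matter. The rule acts in every arm, so its net direction depends on which arm has more gaps before death. It also moves deaths that occurred after Day 15 back to Day 15, which could hide a treatment effect that delays death. The Day 15 category table could then disagree with the death listings planned in SAP Appendix A (Listings 2.6.1 and 2.6.8).

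The analyses exposed are the Day 15 proportional odds model (ITT and PP), the Cochran-Mantel-Haenszel sensitivity test, the Day 15 mean change and the tabulation by study day.

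**Working it through.** No figure in the documents depends on this rule, so there is nothing to reproduce. The check applies the text to a record and then sizes the effect.

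**Which rule governs.** A day before death is not missing because of death, so the death sentence does not reach it. The gap rule does, if a death counts as a nonmissing observation. Protocol 9.3.1 supports that reading: each day's worst score is recorded and death is on the scale, so the day of death is a recorded 8.

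**Worked record.** Scores are 6 through Day 12 and 5 on Day 13. Days 14 to 16 are missing and death is on Day 17. The participant is not discharged, so the lost-to-follow-up sentence does not apply.

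| Handling | Day 13 | Day 14 | Day 15 | Day 16 | Day 17 |
|---|---|---|---|---|---|
| Gap rule as written | 5 | 8 | 8 | 8 | 8 |
| 8 only from date of death, earlier gap set to 7 | 5 | 7 | 7 | 7 | 8 |
| Last living score carried forward | 5 | 5 | 5 | 5 | 8 |

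**Effect of one case.** SAP 3.3 fixes the final analysis at 211 participants. The 2:2:1 ratio implies 211 × 1/5 ≈ 42 on placebo and 211 × 2/5 ≈ 84 per ruxolitinib arm; the documents do not state actual arm sizes. One case is 1/42 = 2.4 points or 1/84 = 1.2 points of the Day 15 death share.

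**Improvement rates.** Protocol 6.1 requires intubation and invasive ventilation at entry, so baseline is 6 or 7. Neither 7 nor 8 is an improvement on either. Setting the gap to 7 therefore leaves the 1- and 2-point improvement rates unchanged. Carrying forward the 5 would change them.

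**How many cases.** The documents give no missingness rate, so the rates below are assumptions. Deaths are also assumed uniform over Days 2 to 29. Mortality M runs from 40% to 60%, the planning values in SAP 3.3. Those values are for ruxolitinib and placebo respectively, so the 2:2:1 planning mix is 0.8 × 40% + 0.2 × 60% = 44%.

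1. Independent daily missingness m. Death on day d needs Days 15 to d − 1 all missing. The expected count is 211 × (M/28) × Σ m^(d−15), summed over d = 16 to 29.
   - M = 40%, m = 2%: 211 × 0.01429 × 0.0204 ≈ 0.06.
   - M = 60%, m = 20%: 211 × 0.02143 × 0.25 ≈ 1.1.
   - M = 44%, m = 2% to 20%: 0.07 to 0.83.
2. One continuous gap, from Day 15 or earlier up to death, in a share f of those dying on Days 16 to 29. The expected count is 211 × M × 14/28 × f.
   - M = 40%, f = 5%: 2.1.
   - M = 60%, f = 20%: 12.7.
   - M = 44%, f = 5% to 20%: 211 × 0.44 × 0.5 × f ≈ 2.3 to 9.3.

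**The case against.** **A death may not be an observation.** SAP 7.4.2 speaks of values missing through death being imputed to 8, so an 8 could be seen as imputed rather than observed. The gap before death would then have one neighbour. This stands as a possible reading, but it leaves the gap with no rule, and the same added sentence resolves it.

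**Gaps should be rare.** Scoring is daily, Day 15 has its own visit with telephone as fallback, and SAP 7.3.1 considers loss unlikely among those still in hospital. This largely stands. The larger counts above need continuous gaps, and no document supports a rate for them. Such gaps are possible, however: Protocol 10.1.1 does not list the ordinal scale in the minimum data after treatment discontinuation.

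**Worst-case handling is a design choice.** SAP 7.4.1 gives zero event-free days to anyone who dies by Day 29. That is a stated definition of a composite count. The ordinal score describes status on a given day, and 7 already is the worst status of a living participant.

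**Stronger inferences that the documents do not support.**

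- A reader might take a participant discharged on Day 12 with score 2, not reached by telephone and dead on Day 20, as certain to score 8 on Day 15. The lost-to-follow-up sentence competes there. Protocol 10.1.4 defines that status by failure of contact, which does not clearly cover a participant whose death becomes known, and the SAP does not rank the two rules.
- A reader might infer shifts of six or seven categories and distorted improvement rates. Against a cap at 7 the shift is one category and improvement rates do not move.
- A reader might call every such 8 known to be false. SAP 4.1.5 imputes some partial death dates, in one case to the day after the participant was last known alive, so vital status in the gap is then not known from data.

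**Conclusion.** The point holds as a defect in one missing-data rule for a secondary endpoint. On the plain text, SAP 7.4.2 can score a living participant as dead on Day 15; on the alternative reading it has no rule for the gap.

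The consequence is limited. The primary endpoint, death through Day 29, does not use the rule. Day 29 is the last scheduled score and normally has no later neighbour. Secondary endpoints carry no multiplicity-controlled claim (SAP 3.2).

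The likely number of cases is small: about one or fewer if daily missingness is independent at 2% to 20%, and more only if long gaps before death are common. Both statements rest on assumed missingness and uniform death times, and the per-case shares of 1.2 and 2.4 points rest on arm sizes inferred from the ratio. It is worth correcting because the stated rule can contradict the trial's own death dates and the correction is cheap.

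**What to change.** Amend SAP 7.4.2 before unblinding to state that:

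1. Category 8 is assigned only on and after the date of death, as derived under SAP 4.1.5 when the date is partial.
2. Missing days between the last observation and death are set to 7, the worst living category. This keeps the worst-case intent.
3. This rule, and not the lost-to-follow-up sentence, applies to discharged participants whose death is later known.

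Report the number of imputed Day 15 scores by arm, and show a sensitivity analysis that carries forward the last living category.

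The cost is a few lines of text, one condition in the derivation and one extra run. The cap changes affected Day 15 scores from 8 to 7 and nothing else at Day 15. Its small drawback is that 7 may still overstate severity for someone who had left hospital, which is what the sensitivity analysis would show.
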